3.6. Adverse Events

3.6.1. Method of Determining Adverse Events

Safety assessments will include recording AEs reported spontaneously by the subject or collected by the Investigator. AEs will be recorded at each visit throughout the study on the appropriate CRF. Every attempt should be made to describe the AE in terms of a diagnosis. If a clear diagnosis has been made, individual signs and symptoms will not be recorded unless they represent atypical or extreme manifestations of the diagnosis, in which case they should be reported as separate events.

Subjects should be asked whether, since the time of the last observation or visit, they had any of the following:

- Experience any changes in well-being;
- Used any new medications;
- Changed medication regimens (both prescription and OTC); and/or
- Were admitted to a hospital or had any accidents.

All questions should be of a general nature and should not suggest symptoms.

When an AE is suspected, all relevant evaluations will be carried out and appropriate treatment provided. Additional follow-up will be done as necessary ([Section 3.6.4](#)) and recorded in the subject's source documents, and the results will be provided to the Sponsor.

For AE definitions and reporting requirements refer to [Section 3.6.2](#) and [Section 3.6.3](#).

Note: Any observed response which can be denoted using the irritation criteria summarized in [Table 3](#) and [Table 4](#) will not be considered an AE. Likewise, any tape-related irritation will only be noted as an AE when all patches are discontinued due to tape reaction around all sites (see [Section 3.6.6](#)).

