3.6.2. Adverse Event Definitions

3.6.2.1. Adverse Events

Information about all local and systemic AEs, whether volunteered by the subject, discovered by Investigator questioning, or detected through other means, will be collected and recorded on the AE CRF and followed as appropriate.

An AE is defined as any untoward medical occurrence in a patient or clinical investigation subject administered a pharmaceutical product (or cosmetic product), which does not necessarily have a causal relationship with this treatment. An AE can therefore, be any unfavorable and unintended sign, symptom, or disease temporally associated with the use of a medicinal investigational product, whether or not considered related to the medicinal investigational product.

Adverse Events will be coded using the Medical Dictionary for Regulatory Activities (MedDRA).

Medical conditions/diseases present before starting study treatment are considered AEs only if they worsen after starting study treatment (any procedures specified in the protocol). Any AEs occurring before starting study treatment but after signing the ICF are recorded on the Medical History/Current Medical Conditions CRF.

To the extent possible, each AE will also be described by:

1. its duration (start and end dates),
2. the severity grade (mild, moderate, severe)
3. its relationship to the study drug,
4. the action(s) taken, and
5. as relevant, the outcome.

Note: Any observed response which can be denoted using the irritation criteria summarized in [Table 3](#) and [Table 4](#) will not be considered an AE. Likewise, any tape-related irritation will not be noted as an AE.

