3.6.2.2. Serious Adverse Events

A “SAE” is any AE that:

- Results in death;
- Is life-threatening (Note: the term “life-threatening” refers to any AE that, as it occurs, puts the subject at immediate risk of death. It does not refer to an AE that hypothetically might have caused death if it were more severe).

- Results in hospitalization or prolongation of current hospitalization (not including hospitalization for a pre-existing condition that has not increased in severity or frequency from the subject's underlying medical condition prior to entry into the study).
- Is a congenital anomaly/birth defect in the offspring of a subject.
- Is another serious (important medical events) event.
- Results in persistent or significant disability/incapacity.

(Note: Important medical events may not be immediately life-threatening or result in death or hospitalization but may be considered serious when, based on the appropriate medical judgment, they may jeopardize the subject or require medical or surgical intervention to prevent one of the outcomes listed above. Examples of such medical events include allergic bronchospasm requiring intensive treatment in an emergency room or at home; blood dyscrasias or convulsions that do not result in inpatient hospitalization; or development of drug dependency or drug abuse.)

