3.6.3. Reporting Adverse Events

Adverse events that occur from the time of first dose through completion of the last study visit should be reported. All SAEs, regardless of causality, occurring from the time of informed consent until 30 days following study completion OR until 30 days after the subject's last application of study medication, whichever is longer, must be reported to TKL Clinical Safety within 24 hours of the knowledge of the occurrence (this refers to any adverse event that meets any of the aforementioned serious criteria). SAEs occurring after the 30-day follow-up period AND considered related to study drug must also be reported to the Sponsor.

Every attempt should be made to describe the AE in terms of a diagnosis. If a clear diagnosis has been made, individual signs and symptoms will not be recorded unless they represent atypical or extreme manifestations of the diagnosis, in which case they should be reported as separate events. If a clear diagnosis cannot be established, each sign and symptom must be recorded individually.

Any SAEs occurring in a subject receiving study drug must be reported to the Sponsor within 24 hours of the site being informed of the event, even if the event does not appear to be drug-related. The report must be made by sending a completed SAE Report form to the Sponsor. Any pertinent follow-up information should be provided in a similar manner. Contact information is provided in [Section 3.7.1](#).

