3.6.6. Expected Adverse Events

Any observed response in the patch test area that can be denoted using the irritation criteria summarized in [Table 3](#) and [Table 4](#) will not be considered an AE.

Tape related reactions will only be recorded as AEs when the subject is discontinued due to tape reaction around all sites. When 1 or 2 sites are experiencing severe tape related reactions, the application site will be stopped and the subject will continue on the study. This will be noted in the database as "T" as indicated in [Table 5](#) and will be considered an expected AE. When all application sites are experiencing tape reaction, the subject is discontinued and therefore be recorded as an AE. The subject will be followed up through resolution.

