3.7.2. Reporting Responsibility

Any death, SAE, pregnancy, (see [Section 3.6](#)), or unusual frequency of AEs, must be reported immediately (i.e., not later than 24 hours after first learning of its occurrence) to the Sponsor's study manager by the Investigator, even if the event(s) appear to be unrelated to study treatment. Follow-up information about a previously reported SAE or pregnancy must also be reported to the Sponsor within 24 hours of receiving it. If the SAE or pregnancy has not been previously documented (i.e., is a new occurrence) and it is thought to be related to the investigational product (or therapy), the Sponsor may contact the Investigator to obtain further information. If warranted, an investigator alert may be issued, to inform all Investigators involved in any study with the same product (or therapy) that this SAE or pregnancy has been reported.

The IRB should also be notified of SAEs or pregnancies and of any follow-up information in writing, as is practical, and depending on local regulations.

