4.6.2. Adverse Events

Adverse events will be summarized as an overall incidence of at least one event, incidence within body systems only, incidence by body system and preferred term, and by highest severity. Each subject will contribute only once (e.g., the first occurrence) to each of the rates, regardless of the number of occurrences (events) the subject experiences.

Treatment-emergent AEs will be summarized and tabulated by the system organ class and preferred term, by severity (mild, moderate, severe) and by relationship to study product (Yes or No).

Treatment-emergent will be defined as any AE with an onset date on or after the first study product administration date. Any event with a missing onset date will be included as a treatment-emergent AE.

Deaths and SAEs will be listed by subject.

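### The rule that scored patch-site responses are not AEs has no exception for a serious reaction, and the tape-reaction recording statements contradict each other

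*Combined protocol and SAP*

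**What the plan says.** **Scored responses.** The exclusion from AEs appears three times. Section 3.6.1 has "Any observed response which can be denoted using the irritation criteria summarized in" Tables 3 and 4, and Section 3.6.2.1 repeats this as a note to the AE definition. Section 3.6.6 has "Any observed response in the patch test area that can be denoted using the irritation criteria summarized in" the same tables. Table 3 runs up to vesicular eruption and a strong spreading reaction; Table 4 includes exudate and erosions.

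**Serious events.** Section 3.6.2.2 defines an SAE as an AE that meets at least one listed criterion. The criterion most open to judgment is "Is another serious (important medical events) event". Section 3.6.3 sets the 24-hour rule and explains that "this refers to any adverse event that meets any of the aforementioned serious criteria". Section 3.7.2 requires immediate notice of "Any death, SAE, pregnancy" and unusual AE frequency. Section 4.6.2 adds: "Deaths and SAEs will be listed by subject".

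**Tape reactions.** Section 3.6.1: a scored response "will not be considered an AE. Likewise, any tape-related irritation will only be noted as an AE when all patches are discontinued" because of tape reaction around all sites. Section 3.6.2.1: a scored response "will not be considered an AE. Likewise, any tape-related irritation will not be noted as an AE". Section 3.6.6 first restricts AE recording to subjects discontinued for tape reaction around all sites. It then says that a severe reaction at one or two sites stops that application site, is entered as T, and counts as an expected AE.

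**The concern.** The study reads out safety in two ways: the irritation scores, and AEs (Section 2). Keeping ordinary scored irritation out of the AE record is sensible, because it is the endpoint and would otherwise be counted twice. But the exclusion is absolute, and serious-event reporting rests on AE status. If a response is not an AE, it cannot on the wording become an SAE. Someone following the text exactly could leave a medically important local reaction out of both the expedited report and the SAE listing.

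For tape reactions, the same event can be an AE or not, depending on which section is followed. That decides whether it enters the AE summaries in Section 4.6.2 and whether the follow-up provision for ongoing AEs in Section 3.6.4 applies.

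**Working it through.** No arithmetic applies, and the plan states no figure to reproduce. The check sets the statements side by side.

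**Serious local reaction, followed through the text**

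1. Is a patch-site response describable by Tables 3 and 4 an AE? Sections 3.6.1, 3.6.2.1 and 3.6.6 all say no. Section 3.6.6 confines the rule to the patch test area and the other two do not; none mentions seriousness.
2. Can it be an SAE? Section 3.6.2.2 requires it to be an AE first. Literal answer: no.
3. Does the 24-hour rule reach it? Section 3.6.3 covers adverse events meeting a serious criterion. Literal answer: no.
4. Is there another route? Section 3.7.2 names death and pregnancy separately, so those are reported whatever their AE status. It has no separate entry for a serious local reaction.
5. Would it be listed? Section 4.6.2 lists deaths and SAEs. Literal answer: no, unless the subject died.

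No seriousness exception was found elsewhere in the AE sections.

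**Tape reaction, by number of affected sites** (each subject has four, Section 3.1)

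| Case | 3.6.1 | 3.6.2.1 | 3.6.6 | Result |
|---|---|---|---|---|
| One or two sites, not severe | not an AE | not an AE | not an AE | agree |
| One or two sites, severe | not an AE | not an AE | not recorded as an AE by its first tape sentence; an expected AE by a later one | conflict, including within 3.6.6 |
| Three sites | not an AE | not an AE | not an AE by its first tape sentence; site handling not addressed | agree on status; gap in handling |
| All four, patching or subject discontinued | AE | not an AE | AE | conflict |

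The all-sites conflict is direct: Section 3.6.2.1 cannot be followed together with the other two. The severe one-or-two-site conflict is one of labelling, but Section 4.6.2 does not say whether an expected AE is tabulated.

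**The case against.** **The serious-reaction gap may be close to empty.** An important medical event turns on jeopardy to the subject or the need for intervention, and neither is a Table 3 or Table 4 descriptor. The examples in Section 3.6.2.2, such as bronchospasm and convulsions, are not patch-site signs. Patches are 2 x 2 cm, and the Days 2-21 procedure re-applies them at a score of 2 or less. The Synopsis and Section 3.6.2.1 also ask for all local AEs, so many investigators would report such a reaction anyway. This stands as an argument that the case is rare. It does not remove the gap: the thing being judged would be the scorable reaction itself, and the note in Section 3.6.2.1 qualifies the general sentence that precedes it. The wording in Sections 3.6.1 and 3.6.3 about atypical or extreme manifestations does not help either. It concerns when to record signs separately from a diagnosis already entered as an AE.

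**A stronger reading is tempting.** A reader might infer that every serious consequence of a patch reaction goes unreported, hospitalization included. The documents do not support that. Death has its own route. Hospitalization, disability and systemic reactions are not things the tables can describe, and Section 3.6.1 has subjects asked about hospital admission. How many of the seriousness criteria are exposed depends on how strictly the notes are read, so no fraction is offered.

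**The tape conflict may be looser than it looks.** Section 3.6.1 refers to Section 3.6.6 for detail, and Section 3.6.6 sends the smaller case to a T notation. That softens the severe one-or-two-site conflict to a matter of labels. It leaves Section 3.6.2.1 in plain contradiction with the other two at all sites.

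**Conclusion.** Both parts hold, at modest size.

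On serious reactions, all three statements of the exclusion lack a seriousness exception, and SAE status rests on AE status. A scorable local reaction judged serious, most plausibly as an important medical event, is outside SAE reporting and the SAE listing on a literal reading. This assumes that an investigator follows the notes as written. The event would be rare, and nothing in the documents allows its frequency to be estimated.

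On tape reactions, there is a firm contradiction when all sites are affected, an inconsistent label for severe reactions at one or two sites, and silence on handling at three. A reader might infer that the sections disagree for every tape reaction. They do not: for non-severe reactions at one or two sites all three give the same answer, not an AE.

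The consequences are confined to AE and SAE recording, reporting and tabulation. The mean cumulative irritation score, its analysis of variance and the sample size are unaffected. Leaving non-serious scored irritation out of the AE record is a reasonable design choice and is not criticised here.

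**What to change.** 1. In Sections 3.6.1, 3.6.2.1 and 3.6.6, add the same sentence after the exclusion: *A patch-site response that meets a criterion in Section 3.6.2.2 is reported as an AE/SAE even if Table 3 or Table 4 can denote it.* Non-serious responses stay excluded, so the endpoint is not counted again as AEs.
2. The sponsor should reconcile the tape wording in the same three sections into one recording statement. It should give the AE status for one, two, three and four affected sites, say whether severity changes that status, and say whether an expected AE enters the Section 4.6.2 tables. Which status applies, and how sites are handled when three are affected, is for the sponsor to settle.

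The cost is one sentence in three places and one reconciled statement. Visits, sample size and the primary analysis do not change. The downside is possibly a few more AE or SAE records.

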3.6.2. Adverse Event Definitions

3.6.2.1. Adverse Events

Information about all local and systemic AEs, whether volunteered by the subject, discovered by Investigator questioning, or detected through other means, will be collected and recorded on the AE CRF and followed as appropriate.

An AE is defined as any untoward medical occurrence in a patient or clinical investigation subject administered a pharmaceutical product (or cosmetic product), which does not necessarily have a causal relationship with this treatment. An AE can therefore, be any unfavorable and unintended sign, symptom, or disease temporally associated with the use of a medicinal investigational product, whether or not considered related to the medicinal investigational product.

Adverse Events will be coded using the Medical Dictionary for Regulatory Activities (MedDRA).

Medical conditions/diseases present before starting study treatment are considered AEs only if they worsen after starting study treatment (any procedures specified in the protocol). Any AEs occurring before starting study treatment but after signing the ICF are recorded on the Medical History/Current Medical Conditions CRF.

To the extent possible, each AE will also be described by:

1. its duration (start and end dates),
2. the severity grade (mild, moderate, severe)
3. its relationship to the study drug,
4. the action(s) taken, and
5. as relevant, the outcome.

Note: Any observed response which can be denoted using the irritation criteria summarized in [Table 3](#) and [Table 4](#) will not be considered an AE. Likewise, any tape-related irritation will not be noted as an AE.

3.6.2.2. Serious Adverse Events

A “SAE” is any AE that:

- Results in death;
- Is life-threatening (Note: the term “life-threatening” refers to any AE that, as it occurs, puts the subject at immediate risk of death. It does not refer to an AE that hypothetically might have caused death if it were more severe).

- Results in hospitalization or prolongation of current hospitalization (not including hospitalization for a pre-existing condition that has not increased in severity or frequency from the subject's underlying medical condition prior to entry into the study).
- Is a congenital anomaly/birth defect in the offspring of a subject.
- Is another serious (important medical events) event.
- Results in persistent or significant disability/incapacity.

(Note: Important medical events may not be immediately life-threatening or result in death or hospitalization but may be considered serious when, based on the appropriate medical judgment, they may jeopardize the subject or require medical or surgical intervention to prevent one of the outcomes listed above. Examples of such medical events include allergic bronchospasm requiring intensive treatment in an emergency room or at home; blood dyscrasias or convulsions that do not result in inpatient hospitalization; or development of drug dependency or drug abuse.)

3.6.2.3. Severity of Adverse Events

“Severity” of the AE refers to the extent to which an AE affects the subject’s daily activities and differs from “Serious,” which is a regulatory classification.

The Investigator is to classify the severity of an AE according to the following definitions:

- **Mild:** The symptom has a negligible effect or no impairing effect on the subject’s normal function.
- **Moderate:** The symptom impairs the subject’s normal function to some extent.
- **Severe:** The symptom has an obvious, significantly impairing effect on the subject’s normal function.

3.6.2.4. Relationship of Adverse Events to Study Treatments

The Investigator is to classify the drug relationship of an AE according to the definitions outlined in [Table 6](#).

Table 6: Relationship of AE to Study Drug

Association	Definition
Not related	(1) the existence of a clear alternative explanation (e.g., mechanical bleeding at surgical site) or (2) non-plausibility, e.g., the subject is struck by an automobile or cancer developing a few days after drug administration.
Unlikely	There is no medical evidence to suggest that the AE may be related to study drug usage, or there is another more probable medical explanation.
Possible	There is medical evidence to suggest that there is a reasonable possibility that the AE may be related to study drug usage. However, other medical explanations cannot be excluded as a possible cause.
Probable	There is strong medical evidence to suggest that the AE is related to study drug usage.
Definite	A clinical event, including laboratory test abnormality (if applicable), in which there is no uncertainty in its relationship to test drug (e.g., positive Rechallenge).

3.6.3. Reporting Adverse Events

Adverse events that occur from the time of first dose through completion of the last study visit should be reported. All SAEs, regardless of causality, occurring from the time of informed consent until 30 days following study completion OR until 30 days after the subject's last application of study medication, whichever is longer, must be reported to TKL Clinical Safety within 24 hours of the knowledge of the occurrence (this refers to any adverse event that meets any of the aforementioned serious criteria). SAEs occurring after the 30-day follow-up period AND considered related to study drug must also be reported to the Sponsor.

Every attempt should be made to describe the AE in terms of a diagnosis. If a clear diagnosis has been made, individual signs and symptoms will not be recorded unless they represent atypical or extreme manifestations of the diagnosis, in which case they should be reported as separate events. If a clear diagnosis cannot be established, each sign and symptom must be recorded individually.

Any SAEs occurring in a subject receiving study drug must be reported to the Sponsor within 24 hours of the site being informed of the event, even if the event does not appear to be drug-related. The report must be made by sending a completed SAE Report form to the Sponsor. Any pertinent follow-up information should be provided in a similar manner. Contact information is provided in [Section 3.7.1](#).

3.6.4. Adverse Event Follow-up

Any ongoing AE at the time of study completion or withdrawal will be followed until the AE is resolved or the subject is referred to his/her own PMD. The Investigator and the Sponsor will decide if longer follow-up is appropriate on a case-by-case basis. Subjects who experience any clinically significant AE will remain under medical supervision until the Investigator or the Sponsor's Medical Monitor deems the AE to be resolved, stabilized, or no longer serious enough to warrant follow-up.

3.6.5. Pregnancy reporting

Prior to study enrollment, females of childbearing potential must be advised of the importance of avoiding pregnancy during study participation and the potential risk factors for an unintentional pregnancy. The signed Informed Consent Form must document this discussion.

A UPT will be performed on all females of childbearing potential at Day 1 (day of first patch application) and EOS. All women of childbearing potential will receive a UPT prior to the first study drug administration and the study drug must be withheld until the results of laboratory pregnancy testing are available. If pregnancy is confirmed, the subject must not receive any study drug and must not be enrolled in the study.

